c. *Psychiatric diagnosis:* The Structured Clinical Interview for DSM-IV (SCID-I/P) (First et al. 1997) will be used to classify subjects according to the presence or absence of major psychiatric disorders including AD. This, together with the physician's unstructured psychiatric interview (visit 2), will be used to assess exclusion criteria for serious psychiatric disorders. The SCID-I/P will be administered at screening visit and the alcohol portion of the SCID will be administered at treatment end-point and the 2, 4, and 6-month follow-up visits to evaluate presence of current alcohol dependence criteria after treatment.

d. *Family history of alcohol dependence:* This interview systematically questions an informant about the presence of psychiatric illness in relatives. We will use the alcohol section of the Family History Assessment Module FHAM (Rice et al. 1995) the subject will be asked to provide information concerning his biological relatives history of alcohol use, however, names of family members will not be obtained.

Table 1: Schedule of Assessments

Study Visit	V 1 Screening	V 2 Baseline	Bi-weekly phone call	V 3-7	V 8 End-point	V 9: 2-mo follow-up	V 10: 4-mo follow-up	V 11: 6- mo follow-up
Time relative to Medication		Start medication	wks 1,3,5	wks 2, 4,6,8,10	Wk 12 End medication			
Medical History, SCID, Fam Hx, Clinical lab tests, blood for DNA	X							
Timeline Follow-Back Interview	X	X		X	X	X	X	X
Vital signs & weight	X	X		X	X			
Alcohol Effects Questionnaire	X				X		X	X
Study outcome blood samples	X			wk 6	X	X	X	X
Physical Exam & Clinician review of Medical History		X						
Penn Alcohol Craving Scale (PACS)		X		X	X	X	X	X
SIP, DMQ, BDI, STAI		X		wk 6	X	X	X	X

Daily IVR call		X	X	X	X			
Side Effect Checklist			X	X	X	X		
Medical Management		X		X				
MED-Q					X			
Follow-up Interview (Alcohol SCID)					X	X	X	X

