effects derived from prior studies of dutasteride (any ongoing potential medication side effects reported at the 2-month follow-up will be assessed again at 4- and 6-month follow-up visits as needed).

d. Measures of treatment received: Records of all medication taken will be recorded. The study staff will also record the number of contact hours subjects have been exposed to for any treatment outside of the study that is related to their drinking to identify if this variable might need to be considered as a covariate in outcomes analysis.

C.6.b.4. Areas assessed at intake, midpoint, end of treatment and at follow-up visits:

a. Alcohol-related problems: The Short Inventory of Problems (SIP). The SIP is a 15-item instrument derived from the Drinker Inventory of Consequences (DrInC), which was developed for use in Project MATCH as a measure of alcohol-related consequences.

b. Psychological symptoms: a) The Beck Depression Inventory (BDI), a 21-item self-report measure of depressive symptoms, yields a total score that ranges from 0 to 63 (Beck et al. 1961). The BDI is generally regarded as a sensitive self-report measure of depressive symptoms, and will be used to explore the relation between depressive symptoms and treatment. b) The State version of the Spielberger State-Trait Anxiety Inventory (STA), a 20-item self-report questionnaire (Spielberger 1983), will be used to provide concomitant monitoring of anxiety symptoms.

c. Drinking Motives: Drinking motives will be measured with the Drinking Motives Questionnaire [DMQ; (Cooper et al. 1992; Cooper 1994)] to explore potential changes as a result of treatment in drinking motives. This instrument contains 20 items with 4 subscales, drink to a) cope motives (e.g., "Because it helps when you are feeling nervous or depressed"), b) conformity motives (e.g., "Because it helps me fit in"), c) enhancement motives (e.g., "Because it's fun"), and d) social motives (e.g., "Because it makes a social occasion more enjoyable"). The DMQ will be administered at baseline and for those subjects who continue to drink again at midpoint, end of treatment and at the 2,4, and 6-month follow-up visits.

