C.8.a.1. Safety: Safety will be analyzed using categorical outcomes, defined by the type and severity of adverse effects. Summary measures of adverse events (AEs) will be developed by organ system from the adverse event checklist and will be compared for patients receiving dutasteride or placebo using χ^2 analysis. Comparisons will be conducted on 1) the number of patients in each of the two groups who report AEs, 2) the number of patients in each of the two groups who report moderate-to-severe AEs, and 3) the number of patients in each group who discontinue treatment due to AEs. Individual AEs that occur in $\geq 5\%$ of patients in either medication condition will be examined using χ^2 analysis.

C.8.a.2. Efficacy: An important initial consideration will be to identify baseline differences between groups that may have occurred despite the use of urn randomization. The distribution of outcome data will also be examined prior to analysis, to determine the need for transformation and whether parametric analytic methods can be utilized. Successful outcome will be defined in terms of three primary dependent measures: SDs/week, HDDs/week, % of subjects with no HDDs, and % of subjects with non-hazardous drinking (no HDDs and SDs/week <15). Patients will be followed irrespective of whether they continue to receive treatment, so that analysis of both primary drinking measures and secondary outcomes will include all data available for the 12-week treatment period. Data for analyses of drinking outcomes during the 12-week treatment period will come from the daily IVR reports (missing IVR report days which will be coded as the larger of either 5 standard drinks (i.e. a HDD) or the IVR average daily use for the week reporting interval). Analysis of drinking for the 6-month follow-up period will be based on TLFB data collected at each follow-up visit. Secondary outcomes will include mean daily alcohol consumption, %dCDT levels (change relative to baseline), and severity of alcohol-related problems (as measured on the SIP and number of DSM-IV AD criteria).

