Efficacy analyses will be performed using linear mixed models implemented in SPSS. Medication group will be treated as a factor and treatment week as a continuous covariate. An interaction term between medication group and week will be used to evaluate the efficacy of dutasteride compared to placebo in reducing drinking behavior over time. Pretreatment drinking will be controlled for using TLFB drinking data for the month prior to screening as a covariate. Treatment goal (stop vs. reduce drinking) will also be included as baseline covariate. The robustness of results will be evaluated by running the model under three different conditions: 1) all provided information, 2) only completers, and 3) imputation where missing days are coded as HDDs for subjects who fail to complete treatment.

For aim 3, analysis of drinking outcome variables will be repeated by including genotype at the *AKR1C3* rs12529 polymorphism as an additional between-subject factor.

C.8.a.3 Examination of daily measures.

Multilevel models will be used to examine the relations among daily measures of mood, daily event triggers and the frequency of drinking and of heavy drinking (level 1 measures) and their moderation by medication (level 2 measure). To examine how the within-person processes vary across individuals (i.e., cross-level medication interactions), the level 1 parameters are considered as outcomes in the level 2 model. Of specific interest is how the level 1 slopes (e.g., the associations between mood or daily event triggers and heavy drinking) vary as a function of experimental condition (dutasteride vs. placebo). Control variables (baseline heavy drinking, depression symptom score, baseline AD symptom severity) will also be included in level 2 predictive models. The utility of each level 2 predictor will be determined by the significance tests of the level 2 partial regression slopes.

C.8.b. Sample size considerations:

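### The only stated efficacy model, carried over to the SIP, tests change from week 6 to week 12 and leaves the Visit 2 SIP score unused; the plan should name a week-12 SIP comparison adjusted for Visit 2 SIP.

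*Combined protocol and SAP*

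**What the plan says.** - **Outcome.** C.8.a.2 lists among the secondary outcomes "severity of alcohol-related problems (as measured on the SIP and number of DSM-IV AD criteria").
- **Schedule.** Table 1 has a row "SIP, DMQ, BDI, STAI" marked at Visit 2, week 6, Visit 8 (week 12) and all three follow-up visits. C.6.b.4 agrees: "Areas assessed at intake, midpoint, end of treatment and at follow-up visits".
- **Model.** C.8.a.2 states "Efficacy analyses will be performed using linear mixed models implemented in SPSS". Medication group is a factor, treatment week is a continuous covariate, and efficacy is judged by their interaction. That sentence speaks of drinking behaviour. No other method is given for the SIP.
- **Baseline covariates.** There are two: "Pretreatment drinking will be controlled for using TLFB drinking data for the month prior to screening as a covariate", and "Treatment goal (stop vs. reduce drinking) will also be included as baseline covariate".
- **Own-baseline handling.** Among the secondary outcomes, only the serum marker is tied to its own baseline: "dCDT levels (change relative to baseline"). The further control variables in C.8.a.3 ("Control variables (baseline heavy drinking, depression symptom score, baseline AD symptom severity) will also be included in level 2 predictive models") belong to the daily-measure models and do not include the SIP.

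**The concern.** C.6.b notes that less drinking may or may not bring improvement elsewhere, and the SIP is one of the measures that would show it. Two things go wrong if the drinking model is carried over to it.

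First, drinking is reported daily, so a group-by-week slope has twelve weeks of data behind it. The SIP has two on-treatment values. A slope through weeks 6 and 12 is just the difference between them. If dutasteride lowered SIP scores by week 6 and the benefit held, the expected interaction would be zero.

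Second, each man's Visit 2 SIP is collected and given no role. Prior drinking is at best a partial stand-in for it. For a comparison of SIP levels between arms, leaving it out gives away precision that is already paid for.

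**Working it through.** **Inputs from C.8.b:** 80 completers per arm, alpha 0.05, d=0.45, stated power 80%. The other effect sizes mentioned there are 0.37 and 0.30. All three refer to drinking outcomes; none is given for the SIP.

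**Assumed, because the documents give no SIP correlation:** Visit 2 SIP with week-12 SIP, a = 0.3, 0.5 or 0.7; prior drinking with week-12 SIP, b = 0.2 to 0.3; prior drinking with Visit 2 SIP, c = 0.3. Treatment goal is left out of the arithmetic.

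**1. The plan's own figure.** A two-sided t-test with 80 per arm and d=0.45 has power 80.8% (81.2% by the normal approximation). The stated 80% reproduces.

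**2. What the group-by-week term measures for the SIP.** With post-baseline values at weeks 6 and 12 only, it is (effect at week 12 minus effect at week 6)/6 per week. An effect of 0.45 SD at both visits gives 0.45 - 0.45 = 0.

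**3. Whether Visit 2 SIP helps that term.** In SD units, the standard error of the between-arm difference in change is √[(2/80) × 2(1 - r)], where r is the correlation between week 6 and week 12.
- At r=0.5 this is √(0.025 × 1.0) = 0.158. If Visit 2 SIP correlates equally with both visits, its covariance with the change is zero and the figure stays at 0.158.
- With uneven correlations (week 6 with week 12, 0.6; Visit 2 with week 6, 0.6; Visit 2 with week 12, 0.45), the variance of change falls from 0.80 to 0.80 - 0.15² = 0.7775. The standard error goes from 0.141 to 0.139, about 1%.

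**4. Whether it helps a week-12 level comparison.** Effective d = d/√(1 - R²).
- Prior drinking only: R² = b².
- Both covariates: R² = (a² + b² - 2abc)/(1 - c²).
- Example, a=0.5 and b=0.2: R² = (0.25 + 0.04 - 0.06)/0.91 = 0.253. Effective d = 0.45/√0.747 = 0.521, power 90.5%.

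| Week-12 comparison, d=0.45 | Power, b=0.2 | Power, b=0.3 |
|---|---|---|
| No covariate | 80.8% | 80.8% |
| Prior drinking only | 82.3% | 84.3% |
| + Visit 2 SIP, a=0.3 | 84.8% | 86.2% |
| + Visit 2 SIP, a=0.5 | 90.5% | 91.3% |
| + Visit 2 SIP, a=0.7 | 97.7% | 97.9% |

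Relative to prior drinking only, the gain is about 2 points at a=0.3, 7 to 8 at 0.5 and 14 to 15 at 0.7. At a=0.5, power rises from 66-68% to 77-78% for d=0.37, and from 49-51% to 59-60% for d=0.30. With a=0.5 and b=0.25, the week-12 standard error falls from 0.153 to 0.136.

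**The case against.** **The model is not written for the SIP.** True. The paragraph speaks of drinking, and its imputation condition concerns days coded as heavy drinking. Applying it to the SIP is an inference from the SIP's place under Efficacy with no other method named. A reader might infer that the plan commits itself to prior drinking as the SIP's only outcome-type baseline covariate. The text does not go that far. If the model does not apply, the SIP has no stated model and the same sentence is still needed.

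**The planned test would gain nothing.** Also true. A reader might infer that stable differences between men inflate the error of the planned test, so that the power gains above are lost from it. They are not. In a group-by-week contrast, stable differences cancel, provided the mixed model accounts for repeated measures (no covariance structure is stated). The gains belong to a level comparison that the plan does not name, so the fix has to name it.

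**Visit 2 SIP could be entered as week 0.** That would use the baseline and recover early effects. Nothing says it will be done.

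**Baseline balance is protected.** A reader might infer that an unadjusted baseline difference could readily pass for a treatment effect, or hide one. The documents do not support that strength of warning. The urn in C.3.c includes number of DSM-IV dependence criteria, heavy-drinking frequency and drinks per drinking day, all of which should limit imbalance in SIP. A level imbalance would also fall mainly on the group main effect, not on the interaction. C.8.a.2 further plans to look for baseline differences, though it does not say how they would be handled. None of this removes between-man variation from a level comparison.

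**Conclusion.** The point holds as a modest improvement to one secondary outcome. If the drinking model is used for the SIP, its test reflects only change from week 6 to week 12 and leaves a collected baseline idle. A week-12 comparison adjusted for Visit 2 SIP would capture the effect present at the end of treatment. It would have power of 85-86%, 91% or 98%, against 82-84% with prior drinking alone, at assumed SIP correlations of 0.3, 0.5 and 0.7.

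The direction is secure for any positive correlation that remains after the planned covariates. The size is not, because both the correlations and the use of d=0.45 for the SIP are assumptions. The primary drinking outcomes are unaffected, and no systematic bias is shown.

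**What to change.** Add to C.8.a.2: the treatment effect on the SIP is the adjusted difference between groups at week 12, with the corresponding difference reported at each follow-up visit. It comes from a linear mixed model with visit as a factor, group, group-by-visit terms, and Visit 2 SIP with its interaction with visit, in addition to treatment goal and pretreatment drinking.

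The covariance structure for repeated visits could be stated in the same place. The cost is one sentence and a few degrees of freedom. No assessment is added and the sample size does not change. It should be written in before unblinding.

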breast tissue (0.5% vs. 0.2%). In other clinical studies, daily doses of 5 mg (i.e., 5 times the daily dose in the current proposed study) were administered to 60 subjects for 6 months with no adverse effects beyond those seen at the more commonly used daily dose of 0.5 mg. In studies of normal volunteers, doses of up to 40 mg daily of dutasteride for 7 days have been administered without significant adverse effects. Dutasteride is not currently FDA approved for use in women due to the potential risk of a specific birth defect (reduced size of male external genitalia).

C.3.b. Placebo drug will consist of lactose powder formulated by the Research Pharmacy Service in gelatin capsules indistinguishable from the capsules containing dutasteride.

C.3.c. Medication Randomization and Drug Accountability: The UCHC Research Pharmacy staff will be responsible for medication randomization and dispensing. The Research Pharmacy will enter randomization variables (age, AKR1C3 genotype, frequency of heavy drinking days for the 90-day period prior to screening, number of DSM-IV AD criteria, use of medication for treatment of co-morbid psychiatric condition, and drinks per drinking day from baseline 90-day TLFB) into an urn randomization program and provide to study staff a supply of study drug, as assigned. Although we will monitor capsule counts at each treatment visit, our primary measure of medication adherence will be daily IVR reports (section D.6.b.2). A daily diary method has been shown to yield results that are comparable to those obtained with electronic monitoring ($r = .91$) (Feinn et al. 2003).

C.4. Study Visits:

C.4.a. Visit 1 (Screening Visit): Prior to informed consent, subjects will have a breath alcohol (BrAC) measurement to validate sobriety. Following completion of informed consent, a brief medical and psychiatric history will be obtained by a study research assistant or nurse. Blood and urine samples will be taken for routine clinical laboratory evaluations, drug screening, DNA extraction and measurement of serum outcome measures GGT, %dCDT, the neuroactive steroid metabolite 3α -diolG and testosterone (to monitor for any unexpected negative effects of dutasteride on testosterone in heavy drinkers). Relevant portions of the Structured Clinical Interview for DSM-IV (SCID-I) will be administered by a research assistant to screen out subjects with major mental illness or dependence on other than alcohol or tobacco.

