C.4.b. Visit 2 (Baseline Visit): 7-14 days after the screening visit, eligible subjects will return for a baseline visit where subjects will be trained to record their mood, desire to drink, self-efficacy and daily drinking using the IVR system and a physical examination will be performed by a study physician or APRN and any medication questions reviewed. Subjects will be instructed in use of study medication and given their initial 4 mg dutasteride or placebo dose and instructed to take two capsules (1 mg) daily at home for the remainder of the 12-week treatment period. Subjects will receive study medication for home use at the baseline and at each follow-up visit. At the baseline visit subjects will receive a one-week back-up supply of medication for use in case of lost capsule or need to reschedule bi-weekly follow-up visits. Subjects will be asked to bring unused medication to each follow-up visit for monitoring medication use. The UCHC research pharmacy will randomly assign subjects to dutasteride or placebo using an urn randomization to balance subjects on AKR1C3 genotype, age and baseline alcohol use. Medication will be delivered or picked up from UConn Health IDS pharmacy for distribution to patients during IDS office hours (M-F 7:30am-4pm). For IDS off-hour appointments, medication may be obtained from IDS pharmacy and kept with study staff in a locked cabinet in a locked office in preparation for that appointment. In case a patient has a last minute cancellation or is a no-show, medication can be kept with study staff until the end of the business week. If the product is not distributed to the patient during that time, it will be returned to pharmacy.

C.4.c. Bi-weekly Clinic Visits 3 - 8: A brief Timeline Follow-Back Interview will be performed to track participants' daily alcohol consumption to augment IVR reports of alcohol use (see section D.9.a.2) and a trained research staff member will deliver the medical management intervention. Blood samples for study outcome measures (GGT, %dCDT, 3α -diolG, and testosterone) will be obtained at visits 5 and 8 (mid-point and end of treatment). We chose biweekly medication monitoring visits during the treatment period in order to optimize tolerability and thereby enhance treatment retention.

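### The urn balances six variables, but the main efficacy model omits four of them without a reason; adjusting for them is a small, nearly free gain in precision

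*Combined protocol and SAP*

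**What the plan says.** **Allocation.** Section C.3.c lists what the Research Pharmacy enters into the urn program: "age, AKR1C3 genotype, frequency of heavy drinking days for the 90-day period prior to screening, number of DSM-IV AD criteria", and then "use of medication for treatment of co-morbid psychiatric condition, and drinks per drinking day from baseline 90-day TLFB". That makes six variables. Section C.4.b describes the same step more briefly: "using an urn randomization to balance subjects on AKR1C3 genotype, age and baseline alcohol use". It does not mention the AD-criteria count or psychiatric medication.

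**Main efficacy model (C.8.a.2).** This is a linear mixed model with medication group, treatment week and their interaction; the interaction is the term that judges efficacy. Two baseline covariates are named. The first is drinking: "Pretreatment drinking will be controlled for using TLFB drinking data for the month prior to screening as a covariate". The second is the treatment goal: "Treatment goal (stop vs. reduce drinking) will also be included as baseline covariate".

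**Other models.** Genotype is added when the analysis is repeated for Aim 3. Baseline AD severity is a control variable in the daily-process models of C.8.a.3. Age and psychiatric medication appear in no model.

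**Baseline check.** C.8.a.2 opens by saying that the analysts will "identify baseline differences between groups that may have occurred despite the use of urn randomization". It does not say what follows if a difference is found.

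**The concern.** When allocation is steered toward balance on variables that predict outcome, the true sampling variation of the difference between arms shrinks. A model that leaves those variables out does not see this. Their variance stays in the residual, the reported standard error is somewhat too large, and the test is somewhat conservative. Adjusting for the balancing variables recovers that precision.

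The plan gives some reason to think that omitted variables are prognostic. C.1.b relates AKR1C3 genotype to heavy-drinking days in 532 male students, and the pilot in C.1.c reports a genotype main effect on drinking. The Aim 4 models control for AD severity, whereas the main model does not.

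Precision matters here because C.8.b cites earlier effects of d = 0.37 and d = 0.3, both below the d = 0.45 on which the trial is powered. What is at stake is a modest amount of power. The validity of the test is not in question.

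**Working it through.** **1. Urn variables against model terms**

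| Urn variable (C.3.c) | Main efficacy model (C.8.a.2) |
|---|---|
| Age | absent |
| AKR1C3 genotype | absent; added for Aim 3 only |
| Heavy-drinking-day frequency, 90 days | covered in kind by pretreatment drinking (one-month window) |
| Number of DSM-IV AD criteria | absent |
| Psychiatric medication | absent |
| Drinks per drinking day, 90 days | covered in kind, as above |

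Four of the six are missing from the main model, and three of the six from the Aim 3 model.

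**2. The plan's own power figure.** Inputs from C.8.b are 80 per arm, d = 0.45 and α = 0.05. Two-sided testing is assumed, since sidedness is not stated. With SD = 1, power = Φ(d/√(2/80) − 1.96) = Φ(2.846 − 1.96) = Φ(0.886) = 81.2%, against 80% stated. The figure reproduces.

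**3. Comparison of levels between arms.** Let R² be the share of residual outcome variance that the four omitted variables explain beyond the covariates already in the model. The documents do not give it. The one large-sample clue is genotype in C.1.b: F = 4.5 with three groups and n = 532, so η² = 2F/(2F + 529) = 9/538 = 0.017. The other values below are assumptions.

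With s = √(1 − R²), and full balance on the omitted variables:
- power with adjustment = Φ(2.846/s − 1.96)
- power without adjustment = Φ((2.846 − 1.96)/s)
- size without adjustment = 2Φ(−1.96/s)

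| R² | Power, adjusted | Power, unadjusted | Forgone (points) | Size, unadjusted |
|---|---|---|---|---|
| 0 | 81.2% | 81.2% | 0 | 5.0% |
| 0.017 | 81.9% | 81.4% | 0.5 | 4.8% |
| 0.05 | 83.1% | 81.8% | 1.3 | 4.4% |
| 0.10 | 85.1% | 82.5% | 2.6 | 3.9% |
| 0.20 | 88.9% | 83.9% | 5.0 | 2.8% |

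Full balance is a limiting case, because an urn only tilts the assignment probabilities. In simulation of an urn on four factors, the unadjusted size was about 4.6% at R² = 0.10 and 3.9% at R² = 0.20 (Monte Carlo standard error about 0.4 points).

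At d = 0.30 the adjusted power is 47.5%, 48.2%, 49.5%, 51.6% and 56.4% for the same five values of R².

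**4. The group-by-week test.** With complete weekly data, this term is the difference between arms in the men's mean fitted slopes. A baseline variable entered as a main effect shifts a man's level and leaves his slope alone, so the standard error does not move. Generalised least squares with 160 men and 12 weeks gives a ratio of 1.000, adjusted to unadjusted, in every scenario tried.

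If the covariates are crossed with week, they can absorb slope variance. Assume slope SD 0.05 (variance 0.0025) and residual variance 0.4. The sum of squared centred weeks is 143, so the residual contributes 0.4/143 = 0.0028 to the variance of each fitted slope. The ratio of standard errors is √[(0.0025(1 − R²slope) + 0.0028)/(0.0025 + 0.0028)]:
- R²slope = 0.05: 0.988
- R²slope = 0.10: 0.976
- R²slope = 0.20: 0.952

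The reduction is therefore about 1 to 5%, and it is zero if the covariates do not predict slope.

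**The case against.** The strongest reply is that the plan judges efficacy by group-by-week, and that main-effect adjustment gains nothing there. This is correct, and it removes any claim that the stated test loses power as specified. The point survives only for comparisons of levels. Two of the listed primary measures are percentages of subjects, which become comparisons between arms if scored per man over the period. Secondary outcomes such as %dCDT change and SIP score may also be compared as levels. The power figures above are for a continuous outcome and do not carry over directly to the percentages.

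The second reply is that nothing in the documents supports an R² of 10 to 20%. That also stands. Genotype alone is worth about half a point. The pilot p-value of 0.029 comes from 27 men, after exclusion of those abstinent from the outset, with no degrees of freedom stated. It cannot size the joint effect of four variables.

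A reader might infer three stronger points that the documents do not support:

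- *That the analysis ignores most of the randomisation.* This is true by count only. Pretreatment drinking, the covariate that one would expect to matter most, is in the model and stands in for two of the six, though over a different window. Genotype enters for Aim 3.
- *That covariates will be chosen from observed imbalance.* C.8.a.2 says only that baseline differences will be identified, and it names its covariates in advance. The conditional rule in C.5.a concerns treatment received outside the study and not the urn variables.
- *That the omission biases the result or inflates type I error.* In the linear model it does neither; any error runs in the conservative direction.

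Finally, the list in C.4.b can be read as a summary of C.3.c, so aligning the two is editorial.

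**Conclusion.** The point holds as a minor one. Four of the six urn variables are missing from the main efficacy model and no reason is given.

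For a continuous comparison of levels, adjustment takes power from the planned 81% to between 82% and 89% for an assumed R² of 1.7% to 20%. Against the unadjusted analysis under full balance, the power forgone is 0.5 to 5.0 points. The low end rests on the student genotype data and the rest is assumed.

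For the group-by-week test as written, the loss from omitting the variables as main effects is zero. A gain of about 1 to 5% in standard error requires covariate-by-week terms and rests on assumed variance components and complete weekly data. No conclusion of the trial is endangered.

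**What to change.** In C.8.a.2, prespecify the urn variables as covariates in the arm comparisons: age, AKR1C3 genotype, number of DSM-IV AD criteria, psychiatric medication, and the two baseline drinking variables or the matching baseline of each outcome. Where slope is tested, add the covariate-by-week terms, since main effects alone do not help that test. If the sponsor prefers to leave any urn variable out, give the reason. Align the urn list in C.4.b with the six variables in C.3.c.

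The cost is wording and a few degrees of freedom. Every variable is obtained before allocation and already entered by the pharmacy, so no new data are needed.
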